9 DATA MANAGEMENT AND ANALYSIS

9.1 SAMPLE SIZE

180 participants will be recruited in the study, with 45 in each of the four groups. Sample size calculations were performed to detect an effect size suitable for the primary outcomes of pain and function, using the Patient Rated Wrist and Hand Evaluation (PRWHE).

The minimal clinically important difference (MCID) for pain and function in patients with wrist injury using the PRWHE is 14 points with a standard deviation of (Sorensen, Howard, Tan, Ketchersid, & Calfee, 2013). Using a global rating of change as an anchor, a minimum change of 5 points out of 15 is required for patients to reliably detect a notable improvement in symptoms and function at 3 months post intervention. To ascertain a clinically significant change in pain and function perceivable by the patient, the project has been designed to detect a relatively large effect size. It is not necessary to detect small effects in patient outcome scores, as clinically this small change is not perceivable by patients. Effect size (f) was set at 0.29, to allow detection of a medium-large effect.

The statistical test used to analyse outcomes data will be a factorial ANOVA, to analyse fixed effects, special, main effects and interactions. This will allow a comparison of treatment groups

compared to the control (Group A) and also examine the interactions between combination interventions (Group D).

- Effect size (f) = 0.29
- Type-I error (α) rate = 0.05
- Power (1- β err prob) = 80% (0.8)
- Number of groups (n) = 4
- Numerator df ($n - 1$) = 3

The above parameters are entered into sample size calculation software *G*Power* (Version 3.1.9.4), with the result that the study must recruit a minimum of 134 participants to achieve 80% power.

F tests - ANOVA: Fixed effects, special, main effects and interactions

Analysis: A priori: Compute required sample size

Input:	Effect size f	=	0.29
	α err prob	=	0.05
	Power (1- β err prob)	=	0.80
	Numerator df	=	3
	Number of groups	=	4
Output:	Noncentrality parameter λ	=	11.2694000
	Critical F	=	2.6742856
	Denominator df	=	130
	Total sample size	=	134
	Actual power	=	0.8013103

Using historical participant retention at the Brisbane Hand and Upper Limb Clinic as a model, an attrition rate of 25% is anticipated. If 134 is the smallest remaining cohort after attrition (75% retention) required to achieve 80% power, the minimum recruitment sample required would be 179. Due to the balanced study design necessitating even group numbers, the target recruitment sample size is 180 participants, with 45 participants allocated to each group.

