3.1 RESEARCH QUESTION

Do adults with acute tears to the triangular fibrocartilage complex receiving a combination of the hand therapy, thermoplastic splint immobilisation and a corticosteroid injection to the TFCC (Group D) have significantly greater improvement in pain and function, as compared to those receiving just one conservative treatment of either splinting (Group B), or corticosteroid injection (Group C), or the control treatment of hand therapy (Group A)?

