9.3 DATA ANALYSIS

Baseline demographic and clinical data will be reported using descriptive statistics and will be tabulated. Between groups differences in baseline data will be examined using unpaired conventional tests of hypothesis depending on the nature of the data. Between group and within group differences in outcome measures over time will be examined using a priori unpaired and paired conventional tests of hypothesis depending on the nature of the data. Linear mixed effects models will be used to examine the within and between group variability of the four groups. Bonferroni adjustments for multiple comparisons will be made where appropriate to mitigate risk of type-1 error.

The complication rates will be reported in terms of frequency. The frequencies of complications will be compared using statistical analysis such as the Pearson chi-square statistic.

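### Section 9.1 sizes the trial for a 3-df four-group omnibus test, so the stated 80% power at 134 is not the power of the 1-df tests that the protocol plans

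*Protocol*

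**What the plan says.** Section 5 describes a four-arm factorial trial. Section 5.1 gives the arms: hand therapy alone (A), with splint (B), with corticosteroid injection (C), or with both (D). This is a 2×2 layout of splint and injection.

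Section 3.1 asks whether Group D patients "have significantly greater improvement in pain and function, as compared to those receiving just one conservative treatment of either splinting (Group B"; the sentence goes on to name Group C and Group A. Section 3.3 states the matching null and adds a null for the main effects.

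Section 9.1 names the analysis: "The statistical test used to analyse outcomes data will be a factorial ANOVA, to analyse fixed effects, special, main effects and interactions". It adds that this will compare the treatment groups with A and examine the interaction in D. The inputs are "Effect size (f) was set at 0.29, to allow detection of a medium-large effect", "Type-I error (α) rate = 0.05", 80% power, "Number of groups (n) = 4", and a numerator df of 3, obtained as the number of groups minus one. The conclusion is that "the study must recruit a minimum of 134 participants to achieve 80% power". An allowance for 25% attrition then gives 179, raised to 180.

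Section 9.3 adds: "Bonferroni adjustments for multiple comparisons will be made where appropriate to mitigate risk of type-1 error".

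**The concern.** A numerator df of 3 with four groups is the overall test that the four means are not all equal. In a 2×2 factorial each main effect has 1 df and so does the interaction. D versus A, D versus B and D versus C are three further 1-df contrasts. The protocol therefore attaches its 80% to a test that answers none of its stated questions.

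Section 9.1 also leaves open what f = 0.29 measures. It may be the spread of all four means or the size of one factorial effect, and the two give very different power for the same test. The alpha used is an unadjusted 0.05, although section 9.3 foresees adjustment.

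At stake is how a non-significant result would be read. If D versus B or C is not significant, a reader who trusts the 80% may take that as good evidence of no added benefit, when power for that contrast could be far lower.

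**Working it through.** **Inputs.** From section 9.1: f = 0.29, alpha 0.05, four groups and 134 analysed, so 134/4 = 33.5 per group and 134 − 4 = 130 error df. The pattern of means is not given, so two patterns are assumed below. No SD value appears in the text at hand, so effects are in SD units.

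**Reproducing the plan's figure.** λ = N·f² = 134 × 0.29² = 11.2694. With 3 and 130 df the critical F is 2.6743 and power is 0.8013; 133 participants give 0.798. Attrition: 134/0.75 = 178.7, so 179. All of this agrees with section 9.1.

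**Reading 1: f = 0.29 is the size of the single 1-df effect tested** (for a main effect, d = 2 × 0.29 = 0.58). λ is again 11.2694, now with 1 and 130 df and critical F 3.914. Power is 91.5%, and 96 participants would give 80%.

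**Reading 2: f = 0.29 is the four-group effect.** The omnibus λ of 11.2694 is then the sum of the λ values for splint, injection and interaction, so power for each depends on how the total is divided. For a pairwise contrast, λ = d² × 33.5/2 = 16.75·d².

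*Only D differs (0, 0, 0, d).* The SD of the four means is d·√(3/16), so d = 0.29/0.4330 = 0.67.
- Each D contrast: λ = 16.75 × 0.4485 = 7.51; power 77.7%. At 0.05/3, if a family of three is assumed, 62.4%.
- Each main effect and the interaction: λ = 11.2694/3 = 3.76; power 48.6%.
- D beating all three, each at 0.05 (simulation): 58%.

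*Additive effects (0, d/2, d/2, d).* The SD of the four means is d·√(1/8), so d = 0.29/0.3536 = 0.82.
- D versus A: λ = 16.75 × 0.6728 = 11.27; power 91.5%.
- D versus B or C: the difference is 0.41, λ = 16.75 × 0.1682 = 2.82; power 38.5%.
- Each main effect: λ = 11.2694/2 = 5.63; power 65.4%. The interaction is zero by construction.
- D beating all three, each at 0.05 (simulation): 23%.

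**Link to 14 points.** Setting d equal to 14 points implies an SD of 14/0.67 = 20.9 under the first pattern and 14/0.82 = 17.1 under the second. These SDs are back-solved and are not in the document. They show that f = 0.29 corresponds to 14 points only once a pattern is chosen. With an assumed SD of 18, 20, 24 or 28, a 14-point pairwise difference has 88.5%, 81.2%, 65.9% or 52.8% power at alpha 0.05. A 14-point main effect has 99.4%, 98.0%, 91.8% or 81.9%.

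**The case against.** **The calculation is correct and 134 may be ample.** Every printed figure reproduces, so this is not an arithmetic error. A reader might infer that the trial is underpowered throughout, and the document does not support that. Under Reading 1 every 1-df test exceeds 80%, and D versus A has 91.5% under additivity. The opposite inference, that the main effects simply have 91.5%, fails too. That figure needs f to be the single-factor effect; under the two patterns used for the D contrasts the main effects have 49% or 65%.

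**The lowest figure concerns a small difference.** The 38% for D versus B or C is for half the A-to-D gap, or 7 points if that gap is the 14-point minimal important difference. Section 9.1 says small effects need not be detected. This stands: 38% is not the power for a 14-point difference.

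**The Bonferroni family is not fixed.** Section 9.3 adjusts only where appropriate, and a statistical analysis plan may define the family. The division by three is an assumption. A claim that required all three contrasts to succeed would need no adjustment, and sections 3.1 and 3.3 join the comparators with 'or', so joint success is not clearly required.

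**Section 3.3 might describe an omnibus test.** Its last sentence speaks of the means of all groups. But it does so for each main effect, and a main effect here compares two levels. A single four-level factor would have no interaction to examine, and section 9.1 plans one.

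**The missing SD may be a loss in text extraction.** It is not part of the criticism.

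**Conclusion.** The mismatch stands. Section 9.1 obtains 134 for 80% power from a 3-df omnibus test, while the protocol's questions are 1-df main effects, a 1-df interaction and D versus A, B and C. The 80% does not apply to those tests.

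The direction of the error is not fixed by the document. Power at 134 is 91.5% if f = 0.29 is the tested effect itself. If f is the four-group effect, power for the named tests runs from 38% to 91.5% across the two patterns examined, leaving aside the interaction that is zero by construction. Neither pattern reaches 80% for D beating all three (58% and 23%). These figures assume 33.5 analysed per group, a common SD and two-sided alpha 0.05; adjustment would lower them.

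A reader might conclude that the main effects ought to become the primary tests. The document does not settle that: it would change the question asked in section 3.1, and the choice is the sponsor's.

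**What to change.** Restate section 9.1 without changing N:

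- Name the primary contrast or contrasts and compute power with numerator df = 1.
- Say whether f = 0.29 is the single-factor or the four-group effect, and give the SD and pattern of means behind it.
- Use the alpha that will apply after any Bonferroni adjustment.
- Replace the general 80% statement with the resulting power for the main effects, for the interaction, and for D versus A, B and C. Quote 91.5% only with the condition that produces it.
- Make sections 3.1, 3.3 and 9.1 agree on which contrast is primary.

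The cost is protocol wording only, with no added participants. The drawback is that the stated power for the D contrasts and the interaction may look less favourable than the present 80%.

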9.2 DATA STORAGE, MANAGEMENT AND CONFIDENTIALITY

Information about study subjects will be kept confidential and managed accordingly to the requirement of Human Research as determined by the NHMRC Guidelines, and the local ethics review board, the Metro South Human Research Ethics Committee.

The master subject list will be kept strictly confidential on a protected server, only accessible by essential members of the investigative team on a password protected computer. The master list will not be removed from the study site and will record the full name and contact details of all of the participants. This list will only be used to contact participants as required for research follow

up. All electronic data forms will be kept in re-identifiable format using a study-specific numerical identifier. All data will be reported in a non-identifiable format.

9.3 DATA ANALYSIS

Baseline demographic and clinical data will be reported using descriptive statistics and will be tabulated. Between groups differences in baseline data will be examined using unpaired conventional tests of hypothesis depending on the nature of the data. Between group and within group differences in outcome measures over time will be examined using a priori unpaired and paired conventional tests of hypothesis depending on the nature of the data. Linear mixed effects models will be used to examine the within and between group variability of the four groups. Bonferroni adjustments for multiple comparisons will be made where appropriate to mitigate risk of type-1 error.

The complication rates will be reported in terms of frequency. The frequencies of complications will be compared using statistical analysis such as the Pearson chi-square statistic.

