8.3.2 Demographic Information

Basic demographic information will be obtained from the participant after consent, but prior to random allocation of an intervention. This will include:

1. Age and gender;
2. Hand dominance;
3. Primary occupation type;
4. Sports or recreational activities;
5. Compensation status/insurance;
6. Medical history including smoking status and concomitant medical conditions;
7. Details of current and previous trauma to the affected wrist;
8. Current pain medications;
9. Surgical history of both wrists;
10. History of any interventions or therapies used by patients in an attempt to treat the affected wrist

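### Section 9.3 plans significance tests of baseline differences between randomised arms, while the outcome methods named state no baseline adjustment

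*Protocol*

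**What the plan says.** Section 9.3 of the protocol plans two things for baseline data. The first is descriptive: "Baseline demographic and clinical data will be reported using descriptive statistics and will be tabulated". The second is inferential: "Between groups differences in baseline data will be examined using unpaired conventional tests of hypothesis depending on the nature of the data". No purpose is given for the tests, and no action follows from their result.

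For outcomes, three methods are named:

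- Section 9.1: "The statistical test used to analyse outcomes data will be a factorial ANOVA, to analyse fixed effects, special, main effects and interactions".
- Section 9.3: "Between group and within group differences in outcome measures over time will be examined using a priori unpaired and paired conventional tests of hypothesis".
- Section 9.3: "Linear mixed effects models will be used to examine the within and between group variability of the four groups".

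None of these statements mentions a baseline covariate, and the terms of the mixed models are not given. On multiplicity, 9.3 says "Bonferroni adjustments for multiple comparisons will be made where appropriate to mitigate risk of type-1 error", without saying whether this covers the baseline tests.

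Section 8.2 describes randomisation in blocks of 12 and names no stratification factor. Section 8.3.2 lists ten items collected before allocation, among them "Details of current and previous trauma to the affected wrist" and "Compensation status/insurance". Baseline outcome scores, strength and range of motion are recorded as well.

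**The concern.** A significance test asks whether a difference could be due to chance. Between randomised arms the answer is known beforehand: if the allocation was sound, chance is the only source. The test therefore answers no useful question.

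What matters for the treatment comparison is the size of an imbalance multiplied by the strength of the factor's relation to outcome. A p-value measures neither. A variable unrelated to PRWHE can come out significant, and a prognostic one can be imbalanced enough to move a contrast without reaching significance.

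Because 9.3 attaches no consequence to the tests, two misuses are left open: adjusting afterwards for whatever was significant, or treating a non-significant result as evidence that the arms are comparable. The remedy is to fix the covariates in advance, and the outcome methods as written do not state any.

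**Working it through.** **1. The plan's own figure.** Inputs from section 9.1: f = 0.29, alpha = 0.05, four groups, numerator df = 3, power 0.80.

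- Noncentrality = N × f² = 134 × 0.0841 = 11.269.
- Critical F(3, 130) = 2.674, and power = 0.8013. At N = 133 the power is 0.798, so 134 is the minimum.
- With 25% attrition, 134 / 0.75 = 178.7, so 179, rounded to 180 (45 per arm).

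All of this reproduces. It is a calculation without a covariate.

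**2. Chance of at least one significant baseline test.** For m independent tests at 0.05 this is 1 − 0.95^m.

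| m | Probability | Expected number |
|---|---|---|
| 10 | 40% | 0.5 |
| 20 | 64% | 1.0 |
| 30 | 79% | 1.5 |

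The protocol does not state m. Ten is the number of items in section 8.3.2; the larger values allow for outcome scores, strength and motion. Independence is an assumption, and overlapping pain, function and strength measures will violate it.

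**3. What a non-significant test can miss.** With 45 per arm, the largest two-arm difference that is still non-significant is t(0.975; 88) × √(2/45) = 1.987 × 0.211 = 0.42 SD of the baseline variable. If that variable has correlation r with the outcome, an unadjusted contrast shifts by r × 0.42 outcome SD. The documents give no r, so 0.3 to 0.7 is assumed. Results are left in SD units because section 9.1 shows no readable SD for PRWHE.

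The type I error of an unadjusted two-arm test, given a standardised imbalance z on that variable, is P(|r·z + √(1 − r²)·Z| > 1.96), with Z standard normal.

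| Assumed r | Shift at the limit (SD) | z = 1.0 | z = 1.5 | z = 1.95 |
|---|---|---|---|---|
| 0.3 | 0.13 | 5.0% | 6.2% | 7.9% |
| 0.5 | 0.21 | 4.8% | 8.2% | 12.8% |
| 0.7 | 0.29 | 3.9% | 10.1% | 20.2% |

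Every column describes an imbalance that the baseline test would pass. Averaged over all randomisations the error rate is 5%: values above 5% after an unlucky allocation are offset by values below 5% after a balanced one.

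**4. What adjustment would buy.** One prespecified covariate with correlation r reduces the residual SD by the factor √(1 − r²), so f becomes 0.29 / √(1 − r²) and the denominator df at N = 134 falls from 130 to 129.

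| Assumed r | Adjusted f | Noncentrality at 134 | Power at 134 | N for 80% power |
|---|---|---|---|---|
| none | 0.290 | 11.27 | 0.801 | 134 |
| 0.3 | 0.304 | 12.38 | 0.841 | 122 |
| 0.5 | 0.335 | 15.03 | 0.909 | 102 |
| 0.7 | 0.406 | 22.10 | 0.983 | 71 |

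This takes the stated f as referring to the unadjusted outcome SD. If the final model adjusts for baseline in some other way, for instance through the repeated measures, part of the gain is already there.

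**The case against.** The strongest reply is that the baseline tests do no damage by themselves. They do not enter the treatment comparison, a descriptive table is planned anyway, and randomisation keeps the overall error rate at 5%. A covariate list is commonly left to a statistical analysis plan, which is not at hand, and the mixed models in 9.3 may already carry baseline PRWHE. Much of this stands. The lack of a covariate list is not in itself the fault, and the point is of moderate weight.

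The reply does not rescue the tests. They are a method that the protocol states, not a detail it leaves open, so a later plan could drop them only by departing from 9.3. They could be defended as a check on allocation concealment, but the protocol gives them no such purpose.

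Several stronger readings are tempting, and the documents do not support them:

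- *That false positives are certain.* The probability depends on a number of tests that is not stated and on independence. Counting about 28 baseline variables gives 1 − 0.95^28 = 76%, which is still not certainty, and the count is a reader's inference.
- *That the tests replace adjustment.* Section 9.3 does not say so, and nothing in it rules covariates out.
- *That harmful imbalance will be left in the result.* This needs three things together: an unadjusted analysis, a prognostic factor, and an unlucky allocation.
- *That the plan itself treats injury details or compensation status as prognostic.* The secondary objective in 3.2.2 names no factor, 8.3.1 speaks only of exploring relations with clinical examination findings, and 8.3.2 is a list of items to collect.

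**Conclusion.** The point holds in a limited form. The baseline hypothesis tests in 9.3 are uninformative in a randomised trial and should go. At least one nominally significant result is likely if many variables are tested, and a non-significant result can coexist with an imbalance of up to 0.42 SD between two arms of 45.

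The outcome methods as written state no baseline adjustment. If the analysis is in fact unadjusted, the general cost is precision: at 134 analysed, power of 0.80 where one covariate would give 0.84 to 0.98. The particular cost is conditional bias of 0.13 to 0.29 SD when a prognostic factor is imbalanced just short of significance. Both ranges rest on the assumed correlation of 0.3 to 0.7. The unconditional type I error is not affected, and no figure in the sample size section is wrong.

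**What to change.** In section 9.3:

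1. Delete the sentence on testing baseline differences. Keep the descriptive table, shown by arm.
2. State that the primary PRWHE model adjusts for baseline PRWHE, and say how: as a covariate, or through baseline as a repeated measure.
3. State that the model also adjusts for any further prognostic factors, already collected, that the sponsor names before outcome data are seen. Time since injury and compensation status are possible examples; the choice is a clinical one, because the documents do not show that either is prognostic.
4. State that no covariate is added or dropped because of a baseline p-value.

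The outcome analysis described in section 9.1 should be worded to match. The cost is a few sentences and a few model degrees of freedom. No new data are needed, and the target of 180 stays as it is, with any gain in precision kept as a margin.

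### Sections 9.1 and 9.3 conflict on how 12-week PRWHE is analysed: the unadjusted factorial ANOVA that sizes the trial is absent from the analysis section, which names no primary method

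*Protocol*

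**What the plan says.** Section 9.1 (Sample size) is definite: "The statistical test used to analyse outcomes data will be a factorial ANOVA, to analyse fixed effects, special, main effects and interactions". The G*Power output printed there is for that test: effect size f = 0.29, "Type-I error (α) rate = 0.05", 80% power, four groups, numerator df 3, denominator df 130, total sample size 134.

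Section 9.3 (Data analysis) never mentions the ANOVA. It names two other approaches for the outcome measures:

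- Simple tests between and within arms, the exact test being left to the type of data: "Between group and within group differences in outcome measures over time will be examined using a priori unpaired and paired conventional tests of hypothesis".
- A modelling approach, given without its terms: "Linear mixed effects models will be used to examine the within and between group variability of the four groups".

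On multiplicity it says "Bonferroni adjustments for multiple comparisons will be made where appropriate to mitigate risk of type-1 error", with no count of comparisons. For baseline data it says "Between groups differences in baseline data will be examined using unpaired conventional tests of hypothesis".

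Three other places bear on this. Section 3.3 states the null hypothesis wholly between groups: Group D against B, C and A, and equality of group means for the main effects. Section 5 calls the design a four-arm factorial trial. Section 8.3.3 has the questionnaires, PRWHE included, completed at baseline before randomisation.

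**The concern.** The two sections give different answers to the question of which test decides the trial. A factorial ANOVA, a set of two-arm unpaired tests and a mixed model can give different results from the same 12-week scores, and the protocol ranks none above the others. As written, the choice could be made after the results are seen. A later analysis plan would have to overrule one section or the other.

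Two further points follow from the same text.

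- **Baseline PRWHE.** It is available for everyone at no extra cost, yet the analysis on which the trial is sized does not use it. Precision is lost, and any chance imbalance at baseline stays in the treatment estimate.
- **Paired tests.** They are planned as hypothesis tests beside the between-group ones, but they test change over time within an arm. Every arm receives hand therapy, so every arm may improve whether or not splint or injection adds anything.

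**Working it through.** **Step 1. Reproduce the protocol's figure.** Inputs from section 9.1: f = 0.29, alpha 0.05, numerator df 3, four groups.

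- Noncentrality λ = N·f² = 134 × 0.0841 = 11.2694.
- Denominator df = N − 4 = 130.
- Critical F = 2.6743.
- Power = 0.8013 at N = 134, and 0.7979 at N = 133.
- Attrition: 134 / 0.75 = 178.7, so 179, rounded to 180 for equal arms.

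All of this matches the protocol. Because 130 = 134 − 4, only the four group means are fitted. A baseline covariate would leave 129.

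**Step 2. Set the methods side by side.**

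| Method | Named in | Uses baseline PRWHE? | Addresses the section 3.3 null? |
|---|---|---|---|
| Factorial ANOVA | 9.1 only | No (df 130) | Yes |
| Unpaired tests | 9.3 only | Not as a covariate | Yes, two arms at a time |
| Paired tests | 9.3 only | Only as the start of within-arm change | No |
| Linear mixed models | 9.3 only | Not stated | Can do, if a contrast is specified |

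No row is designated primary.

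**Step 3. What baseline adjustment is worth.** The protocol gives no correlation r between baseline and 12-week PRWHE, so I assume 0.3 to 0.7. Adjustment multiplies residual variance by 1 − r². Reading f = 0.29 as the unadjusted effect, λ becomes 11.2694 / (1 − r²) with df 3 and 129.

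| r | 1 − r² | Variance cut | λ | Power at N = 134 | N for 80% power |
|---|---|---|---|---|---|
| unadjusted | 1 | none | 11.27 | 80.1% | 134 |
| 0.3 | 0.91 | 9% | 12.38 | 84.1% | 122 |
| 0.5 | 0.75 | 25% | 15.03 | 90.9% | 102 |
| 0.7 | 0.51 | 51% | 22.10 | 98.3% | 71 |

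An ANOVA of change from baseline does not do the same job. Its variance factor is 2(1 − r), which gives power of about 64%, 80% and 96% at r = 0.3, 0.5 and 0.7. That is below the adjusted model each time.

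**Step 4. What the paired tests would show if no treatment differed.** Suppose all four arms improve by the same 14 points (the protocol's minimal important difference) with 33 analysed per arm. The text gives no SD. If f = 0.29 represents one arm differing from the other three by 14 points, the SD of the means is 6.062 and the implied SD is 6.062 / 0.29 = 20.9. At r = 0.5 the SD of change is 20.9 × √(2 × 0.5) = 20.9, and the noncentrality is 14 / (20.9 / √33) = 3.85.

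- Each paired test is significant with probability about 0.96.
- All four are significant with probability about 0.86 (0.962⁴).

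Other patterns behind f = 0.29 imply an SD from 17.1 to 24.1. Over that range and r = 0.3 to 0.7, the per-arm probability runs from 0.78 to nearly 1, and the all-four probability from 0.37 to nearly 1. The paired tests would often be positive in every arm with no difference between treatments.

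**The case against.** The strongest reply is that model detail belongs in a statistical analysis plan, which is not shown. That stands for the mixed model: section 9.3 does not list its terms, and baseline could enter as a covariate or as a repeated response. A reader might infer that all the named analyses ignore baseline. The text supports this only for the ANOVA and the simple between-arm tests. The reply does not remove the conflict between 9.1 and 9.3, which lies in what the protocol states.

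A reader might also infer that the sponsor will offer within-arm improvement as proof of efficacy. The protocol does not say so, and it plans between-group tests as well. The wording leaves that risk open and goes no further.

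A third tempting reading is that arm-by-arm tests throw away the factorial design, since a main effect compares about 67 with 67 and two arms only about 34 with 34. But sections 3.1 and 3.3 ask whether D beats A, B and C, which are arm-against-arm questions by design. Setting the power of the two side by side compares different quantities, and the main-effect figure speaks for the single-treatment question only if there is no interaction.

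Finally, the gain from adjustment depends on the test. For a main effect of 14 points with an assumed SD of 24.1 (7 / 0.29, two arms differing from the other two by 14), power at 134 is already 91.6% and rises to 97.1% at r = 0.5. That is a gain of 5.5 points, against 10.8 for the 3-df test.

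**Conclusion.** The concern holds as a conflict in the stated text. Section 9.1 fixes and powers an unadjusted factorial ANOVA, while section 9.3 omits it, lists other methods and makes none primary. The paired tests serve no stated hypothesis.

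On baseline, the ANOVA and the simple between-arm tests leave available precision unused. For an assumed r of 0.3 to 0.7 this is 9% to 51% of residual variance, or about 4 to 18 points of power on the stated 3-df test. The direction is certain whenever r is materially different from zero, but the size rests on that assumption. This is lost efficiency, not bias, and nothing here shows the sample size to be wrong: 80% power at 134 is correct for the test named in 9.1.

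The planned significance tests of baseline differences are a minor matter. Under proper randomisation any such difference is due to chance, and testing it does not change the treatment estimate.

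**What to change.** Make 9.1 and 9.3 say the same thing:

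1. **One primary model.** 12-week total PRWHE in a linear model, or the week-12 contrast of a mixed model, with splint, injection, splint × injection and baseline PRWHE, all participants analysed as randomised.
2. **State the primary contrasts.** Choose the marginal main effects, or D against A, B and C, or both, and give the number of comparisons for Bonferroni. Three D contrasts alone would each be tested at 0.05 / 3 = 0.0167. Obtain main effects by effect coding or averaged contrasts. With 0/1 coding and the interaction in the model, the splint coefficient is only B against A. The 80% in section 9.1 belongs to the 3-df overall test and does not carry over to these contrasts.
3. **Within-arm change.** Report it descriptively, without tests.
4. **Baseline table.** Drop the significance tests.
5. **Other models.** Keep them as sensitivity analyses and label them so.

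The cost is protocol and analysis-plan wording. No new data or participants are needed.
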